**PROTOCOL SYNOPSIS**

|                                 |  |
|---------------------------------|--|
| PROTOCOL TITLE:          | An Open-Label, Randomized Phase 2 Trial of AM0010 in Combination with Nivolumab vs Nivolumab Alone as Second-Line (2L) Therapy in Subjects with Stage IV/Metastatic Wild-Type (WT) Non-Small Cell Lung Cancer (NSCLC) and Low Tumor Expression of PD-L1  |
| PROTOCOL NUMBER:         | AM0010-202; J1L-AM-JZGD  |
| CLINICAL PHASE:          | 2  |
| INDICATION:              | Wild-type (without known epidermal growth factor receptor [EGFR] or anaplastic lymphoma kinase [ALK]) non-small cell lung cancer (NSCLC)   |
| NUMBER OF PATIENTS:      | Approximately 50. The enrollment will close once approximately 50 patients have been randomized or by 31 March 2019.   |
| INVESTIGATIONAL PRODUCT: | AM0010 (pegylated IL-10 [pegilodecakin]; LY3500518)  |
| ACTIVE INGREDIENT:       | PEG-rHuIL-10   |
| OTHER DRUG:              | Nivolumab  |
| TRIAL LOCATION:          | Multi-center, USA only   |
| TRIAL DURATION:          | Approximately 36 months after enrolment completion   |
| RESEARCH HYPOTHESIS:     | In patients diagnosed with metastatic NSCLC who have been exposed to 1 prior systemic therapy, not containing anti-PD-1/PD-L1 treatment alone, in combination with an anti-CTLA-4 treatment or in combination with platinum-based chemotherapy, and whose tumors have negative or low PD-L1 expression, the administration of AM0010 in combination with nivolumab increases the objective response rate (ORR).  |

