AM0010 in combination with nivolumab has substantial clinical efficacy in the Phase 1b expansion phase in second-line or greater metastatic NSCLC. Nivolumab is one of several agents that are approved for use upon progression from platinum doublet first-line therapy of NSCLC based on improvements in OS when compared to docetaxel. It is the preferred treatment in the second-line setting and has become the benchmark comparator. Nivolumab was also chosen in this study because its activity vs that of the AM0010 combination with nivolumab will show the contribution of components in this treatment setting.

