### **10.5.3 Efficacy Analyses**

#### **10.5.3.1 Primary Efficacy Analyses**

Objective response rate is defined as the proportion of patients who achieve confirmed CR+PR. Objective response rate and the corresponding 95% exact CI will be calculated by Clooper-Pearson method for each randomized arm.

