#### **10.5.3.2 Secondary Efficacy Analyses**

Progression-free survival time will be summarized using Kaplan-Meier method to estimate the median PFS and 95% confidence interval (CI).

Overall survival will be summarized using Kaplan-Meier method to estimate the median PFS and 95% confidence interval (CI).

The DCR will be analyzed in the same manner as objective tumor response.

Duration of response is defined as the time from the date of the first documentation of objective tumor response (CR or PR), as determined by the Investigator using RECIST v.1.1, that is subsequently confirmed to the date of the first documentation of objective tumor progression or to death due to any cause, whichever occurs first. Duration of response will be censored on the date of the last tumor assessment on trial for patients who do not have objective tumor progression and who do not die due to any cause while on trial. For patients who have an ongoing objective response but discontinued to have tumor scans assessments before disease progression, the duration of response will be censored at the date of the last tumor assessment.

Duration of response will be estimated for each treatment arm using the Kaplan-Meier product-limit method for patients who have CR or PR. Duration of SD will be summarized as well.

Time to response is defined as the time from date of randomization to the date of the first documentation of objective tumor response that is subsequently confirmed. Duration of

response and time to response will only be evaluated in patients with objective response of CR or PR and will be summarized by trial treatment arm.

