## 4. Study Objectives

### 4.1. Primary Objective

The primary objective of Study J1L-AM-JZGD (JZGD) is to evaluate objective response rate (based on RECIST v1.1) in AM0010 plus nivolumab and nivolumab alone in patients diagnosed with metastatic non-small cell lung cancer (NSCLC) who have been exposed to 1 prior systemic therapy, not containing anti-PD-1/PD-L1 treatment alone, in combination with an anti-CTLA-4 treatment or in combination with platinum-based chemotherapy, and whose tumors have negative or low PD-L1 expression. AM0010 is also known as pegilodecakin and LY3500518 and hereafter is referred to only as AM0010.

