## 6. A Priori Statistical Methods

### 6.1. General Considerations

#### 6.1.1. Population

**Enrolled Population:** all patients who signed the informed consent form and were registered into the interactive web response system (IWRS).

**Intent-to-Treat (ITT) population:** all randomized patients per the IWRS.

Unless otherwise noted, all disposition analyses will be performed on the ITT population, all patient characteristic and efficacy analyses will be performed on the ITT population and all safety and exposure analyses will be performed on the safety population.

All analyses will be performed descriptively by treatment arm. Unless otherwise noted, all summary statistics on the ITT population will be performed by assigned treatment arm and all summary statistics on the safety population will be performed by actual treatment received.

**Per-Protocol Population:** all patients who are in the safety population and have no important protocol deviations.

The important protocol deviations which will result in exclusion from the Per-Protocol population are listed below. This is not an exhaustive list and may be amended over the course of the trial.

- patients with disease histology other than NSCLC
- patients with European Cooperative Oncology Group (ECOG) >1 at baseline
- patients who received more than one prior regimen in metastatic setting
- patients who do not have measurable disease at baseline
- patients receiving the incorrect randomized treatment assignment (any amount of duration)

**Response Evaluable Population:** all patients who are randomized and received any amount of study medication, have baseline adequate tumor assessment, and at least 1 post-baseline adequate tumor assessment.

**Safety Population:** all randomized patients who received any amount of study medication, AM0010 or nivolumab.

**PK Population:** all patients who are treated and with available serum time-concentration data from randomized patients.

**Biomarker Population:** all patients who are treated and with available biomarker data from randomized patients.

**ADA Evaluable Population:** all patients who are treated (in safety population), have baseline ADA (Anti-Drug Antibody) result, and at least one post-baseline ADA result.

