#### **6.5.2. Primary Endpoint: Objective Response Rate**

##### **6.5.2.1. Definition**

The primary efficacy measure is ORR as defined by RECIST version 1.1 and determined by the investigator.

The ORR is defined as the number of patients with a complete response (CR) or partial response (PR) divided by the number of randomized patients recorded between the date of randomization and the date of objectively documented progression or the date of subsequent anti-cancer therapy, whichever occurs first. For patients without documented progression or subsequent anti-cancer therapy, all available response designations will contribute to the ORR.

determination. For patients who continue treatment beyond progression due to suspected pseudoprogression is described in the protocol Section 7.6.

Rates and their corresponding 95% exact CI will be calculated by Clooper-Pearson method for each randomized treatment arm.

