The PFS curves for each treatment arm will be estimated using the Kaplan-Meier product-limit method. Two-sided, 95% CI for the first quartile, median, and third quartile of PFS will be provided. Progression-free survival rates at fixed time points (every 3 months) will be estimated using Kaplan-Meier estimates on the PFS curve for each randomized arm provided minimum follow-up is longer than time point to generate the rate. Two-sided 95% CIs for the PFS rates will be calculated.

Restricted mean difference in PFS will be calculated. Following the suggestion of Karrison (1997), the restriction time T will be chosen as largest time point t such that the standard error (SE) of the survival estimate at time t in each treatment group is no more than 0.075. For this purpose, we will use the simple, albeit conservative, formula proposed by Peto et al. (1977) for calculating the SE of S(t) as:

$$SE(S(t)) = S(t)\sqrt{1 - S(t)/n(t)}$$

where n(t) is the number of patients still at risk at time t.

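### The hypothesis is that AM0010 raises ORR, but ORR and DCR are planned only as per-arm rates with no between-arm estimate, and the strata named for analysis have no stratified method

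*SAP*

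**What the plan says.** The research hypothesis in the protocol synopsis is comparative: "the administration of AM0010 in combination with nivolumab increases the objective response rate (ORR"). Protocol 1.3 explains the choice of nivolumab as comparator by saying that "its activity vs that of the AM0010 combination with nivolumab will show the contribution of components in this treatment setting". SAP 4.2 words the secondary objectives, DCR among them, as estimating one arm versus the other.

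The primary objective is worded by arm. SAP 4.1 is "to evaluate objective response rate (based on RECIST v1.1) in AM0010 plus nivolumab and nivolumab alone". SAP 6.1.1 adds a general rule: "All analyses will be performed descriptively by treatment arm". The sample size text (protocol 10.3, SAP 5.2) speaks only of precision within an arm.

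For the analysis of ORR, protocol 10.5.3.1 has "Objective response rate and the corresponding 95% exact CI will be calculated by Clooper-Pearson method for each randomized arm", and SAP 6.5.2.1 has "Rates and their corresponding 95% exact CI will be calculated by Clooper-Pearson method for each randomized treatment arm". For DCR, protocol 10.5.3.2 says "The DCR will be analyzed in the same manner as objective tumor response", and SAP 6.5.3.3 gives a rate and 95% CI for each arm. No difference, ratio or odds ratio is specified for either endpoint.

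For PFS, SAP 6.5.3.1 says "Restricted mean difference in PFS will be calculated". SAP 6.5.3.2 analyses OS in a similar way. No confidence interval is specified for the restricted mean difference, and protocol 10.5.3.2 plans only Kaplan-Meier medians with intervals.

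On strata, protocol 10.5.1 has every efficacy analysis stratified by histology at randomisation. SAP 6.5.1.2 lists histology and smoking history for the primary and secondary analyses, using IWRS values. SAP 6.5.2.2 defines ORR2 as a similar analysis with CRF histology strata, to be run only if IWRS and CRF histology disagree for at least 10% of randomised patients.

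**The concern.** The quantity in the hypothesis is a difference between arms, and the plan never estimates it. A reader can subtract the two printed rates, but the interval around that difference would have to be chosen after the data are known, or replaced by an informal look at whether two per-arm intervals overlap. For DCR the gap is plainer still, because SAP 4.2 itself states a versus objective.

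The stratification text is a second, separate gap. The two documents name different strata, and neither gives an estimator, a weighting or a by-stratum display. A pooled Clopper-Pearson interval for one arm uses no strata. ORR2, if triggered, would therefore return the primary figures again, unless rates within each stratum are meant, which the text does not say. A histology-stratified difference also cannot be recovered from the planned per-arm tables.

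**Working it through.** **1. The plan's own figures.** Inputs: n = 25 per arm and 3, 6 or 8 responders (protocol 10.3, SAP 5.2). Clopper-Pearson limits are the beta quantiles B(α/2; x, n-x+1) and B(1-α/2; x+1, n-x). At 90%:

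| Responders | Computed | Stated |
|---|---|---|
| 3/25 | 3.35% to 28.17% | 3%, 28% |
| 6/25 | 11.01% to 41.95% | 11%, 42% |
| 8/25 | 17.03% to 50.36% | 17%, 50% |

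The stated precision reproduces. It concerns a single arm. No effect size, alpha or power is given, so there is no two-arm sample size to reproduce.

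**2. The missing contrast.** The documents do not assign the example counts to arms; the pairings below are an assumption. The Newcombe interval for d = p1 - p2 uses each arm's Wilson limits (l, u):

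- lower = d - √[(p1 - l1)² + (u2 - p2)²]
- upper = d + √[(u1 - p1)² + (p2 - l2)²]

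The 95% Wilson limits are 4.17% to 29.96% for 3/25, 11.50% to 43.43% for 6/25, and 17.21% to 51.59% for 8/25. For 8 vs 3:

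- lower = 0.20 - √(0.1479² + 0.1796²) = 0.20 - 0.233 = -0.033
- upper = 0.20 + √(0.1959² + 0.0783²) = 0.20 + 0.211 = 0.411

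The last column is exact binomial enumeration, taking the example rates as the true rates (an assumption).

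| Arm 1 vs Arm 2 | Difference (points) | 95% Newcombe | Chance that the interval includes zero |
|---|---|---|---|
| 8 vs 3 | +20 | -3.3 to 41.1 | 58% |
| 6 vs 3 | +12 | -9.9 to 32.9 | 80% |
| 8 vs 6 | +8 | -16.4 to 31.2 | 90% |

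**3. How much the interval method matters.** At 9/25 vs 3/25 (+24 points) the lower limit is +1.3 by Wald, +0.1 by Newcombe and -0.4 by Agresti-Caffo, so the methods can fall on either side of zero. That case lies on the boundary. At the three rate pairs above, in the same order, Newcombe and Agresti-Caffo disagree about zero in 5.3%, 4.2% and 1.4% of trials. Newcombe and Wald disagree in 2.2%, 1.2% and 1.6%.

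**4. What stratifying would change.** The SAP's two factors cross to 2 × 3 = 6 cells: 50/6 = 8.3 patients per cell, about 4 per arm. Histology alone gives two strata.

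Worked example, with an assumed 15 squamous and 35 non-squamous patients: Arm 1 has 2/7 and 6/18 responders, Arm 2 has 1/8 and 2/17. The Mantel-Haenszel weights are 7×8/15 = 3.733 and 18×17/35 = 8.743. The stratum differences are 0.1607 and 0.2157. The pooled difference is (3.733×0.1607 + 8.743×0.2157)/12.476 = 0.199, with Sato 95% interval -2.4 to 42.2 points. The crude difference is +20.0.

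A simulation (200,000 runs per setting) assumed 20-40% squamous, a 25/60/15 smoking mix, permuted blocks of 4, and a squamous minus non-squamous response difference of 0 or 10 points. None of these comes from the documents. The stratified estimate differed from the crude one by 0.3 to 0.7 points on average, and the Sato interval covered 93.7% to 93.9%.

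**The case against.** The strongest reply is that reporting by arm is a declared choice. The primary objective, the sample size text and the SAP's general rule all say so, and neither a research hypothesis nor a sentence on comparator choice defines an estimand. This stands as far as a test is concerned. A reader might infer that the plan wrongly omits a formal comparison, or that the trial is underpowered for one. The documents do not support that, because no test was ever planned and the sizing claims none. It does not dispose of the missing estimate: the same descriptive SAP plans a difference for PFS, and SAP 4.2 asks for a versus estimate of DCR.

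Three further objections stand and limit the point:

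- A reader might infer that PFS and OS have a fully specified contrast. They do not: the OS difference rests on a cross-reference, and neither difference has a stated interval.
- A reader might infer from the 9 vs 3 example that the choice of interval would often change the message. At the plan's example rates it does so in about 1% to 5% of trials.
- ORR2 is conditional on the 10% disagreement rule, and by-stratum rates are a possible reading, so it cannot be called empty outright.

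Timing also matters. The trial is open-label, and SAP section 3 records an interim with an 18 March 2019 cut-off, so a contrast added now may not precede all sight of efficacy by arm.

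**Conclusion.** The point holds in this form: ORR and DCR lack a pre-specified between-arm estimate, although the hypothesis (for ORR) and SAP 4.2 (for DCR) call for one. Separately, the stratification statements conflict between the documents and have no method behind them. It should be corrected, but nothing in the plan is invalidated.

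The size is modest. The difference would be imprecise: about 44 points wide at 8 vs 3 (41.1 + 3.3), and including zero in 58% to 90% of trials if the example rates were true. The main gain is having the difference and its interval method fixed in advance. Stratifying by histology would be expected to move the estimate by under one point on average, under the simulation's assumptions. The direct figures rest on 25 patients per arm and on pairing the plan's own example counts.

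**What to change.** In the SAP:

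1. In 6.5.2.1 and 6.5.3.3, add the Arm 1 minus Arm 2 difference in ORR and in DCR with a two-sided 95% Newcombe interval, labelled descriptive and without a test.
2. In 6.5.1.2, name histology as the analysis stratum, in line with protocol 10.5.1. Add a Mantel-Haenszel difference by IWRS histology with Sato variance as a supportive row, and define ORR2 as that difference using CRF histology.
3. State whether the PFS and OS analyses are stratified, and give a 95% interval for their restricted mean differences, so that the stratification statement matches what is done.
4. Record that the ORR and DCR contrast was added after the 18 March 2019 interim cut-off in an open-label trial. The documents do not show whether the ORR data lock has passed; if it has, say that the contrast was added after lock.

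The cost is a SAP revision and one or two table rows per endpoint, from data already collected, with no extra patients or visits. Items 1 and 2 need no protocol amendment, because protocol 10.5.1 already names histology. If item 3 leaves PFS or OS unstratified, the SAP should record that as a departure from protocol 10.5.1. The drawback is a wide interval that will often include zero and must not be read as a test.

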#### **6.5.2.2. Additional Analysis of ORR**

Objective response rate Analysis 1 (ORR1): the same primary analysis on the primary endpoint ORR will be performed on the response evaluable population.

Objective response rate Analysis 2 (ORR2): If the stratification factor, squamous versus non-squamous, at the IWRS and at baseline (CRF) disagrees for at least 10% for the randomized patients, similar analysis of ORR as primary analysis will be performed using the strata determined at baseline based on CRF.

Objective response rate Analysis 3 (ORR3): the same primary analysis on the confirmed ORR will be performed.

Objective response rate Analysis 3 (ORR4): the same primary analysis on the ORR including response observed beyond pseudoprogression will be performed.

### **6.5.3. Secondary Endpoints**

#### **6.5.3.1. Progression-Free Survival**

##### **6.5.3.1.1. Definition**

Progression-free survival (PFS) is defined as the time from randomization to the date of documented progression (per scan or clinical progression as determined by the investigator) or the date of death due to any cause, whichever is earlier.

The detailed censoring rules are described in [Table JZGD.6.1](#).

**Table JZGD.6.1. Rules for Determining Date of Progression or Censor for Progression-Free Survival (PFS)**

Rule	Situation	Date of Progression or Censor	Outcome
1	No baseline tumor assessments	Date of Randomization	Censored
2	No post baseline assessments and no death	Date of Randomization	Censored
3	No documented progression and no death (with a post-baseline tumor assessment)	Date of last adequate tumor assessment	Censored
4	Patient lost to follow-up (or withdrew consent from study participation) before documented progression or death	Date of last adequate tumor assessment	Censored
5	Progression per scan	Date of documented progression. If a tumor assessment was done on multiple days, use the earliest date for that assessment	Progressed
6	Clinical progression	Date of clinical progression	Progressed
6	Death without documented progression	Date of death	Progressed
7	Documented progression or death after missing $\geq$ two consecutive post-baseline tumor assessments	Date of last adequate tumor assessment before missed assessment or date of randomization, whichever is later	Censored
8	New anti-cancer therapy started without a prior documented progression or death	Date of last adequate tumor assessment before the start of new anti-cancer therapy	Censored
9	Documented progression or death after missing $\geq$ two consecutive post-baseline tumor assessments	Date of last adequate tumor assessment before the start of new anti-cancer therapy	Censored

Note: Progression-free survival and associated outcome is determined by the earliest of the dates above, if more than one situation applies. Two consecutive post-baseline tumor assessments refers to the next 2 protocol scheduled tumor assessments. Time is measured from the last adequate tumor assessment date. The window of the tumor assessment is also considered (that is, the weeks for the scheduled tumor assessments plus the window allowed for each scan is 7 days, for example a patient who goes more than  $(2*7*8+7) = 119$  days is considered missing 2 consecutive assessments) in the first year.

The PFS curves for each treatment arm will be estimated using the Kaplan-Meier product-limit method. Two-sided, 95% CI for the first quartile, median, and third quartile of PFS will be provided. Progression-free survival rates at fixed time points (every 3 months) will be estimated using Kaplan-Meier estimates on the PFS curve for each randomized arm provided minimum follow-up is longer than time point to generate the rate. Two-sided 95% CIs for the PFS rates will be calculated.

Restricted mean difference in PFS will be calculated. Following the suggestion of Karrison (1997), the restriction time T will be chosen as largest time point t such that the standard error (SE) of the survival estimate at time t in each treatment group is no more than 0.075. For this purpose, we will use the simple, albeit conservative, formula proposed by Peto et al. (1977) for calculating the SE of S(t) as:

$$SE(S(t)) = S(t)\sqrt{1 - S(t)/n(t)}$$

where n(t) is the number of patients still at risk at time t.

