### **4.1 Inclusion Criteria**

Eligible patients must meet the following criteria to be enrolled in the trial:

1. Signed Written Informed Consent (ICF). Patients must have signed and dated an Institutional Review Board/Independent Ethics Committee (IRB/IEC)-approved written ICF in accordance with regulatory and institutional guidelines. This must be obtained before the performance of any protocol-related procedures that are not part of normal patient care.
  - a. Patients must be willing and able to comply with scheduled visits, treatment schedule, laboratory tests, and other requirements of the trial.
2. **Target Population**
  - a. Patients must have histologically or cytologically confirmed NSCLC that is Stage IV/metastatic.
  - b. Patients must have received 1 prior systemic therapy that did not include an anti-PD-1, anti-PD-L1, and/or anti-CTLA-4 treatment for the metastatic disease (Stage IV).
  - c. Patients with tumor tissue negative or low expression of PD-L1 as defined by Tumor Proportion Score (TPS) 0% to 49% by any FDA-approved PD-L1 assay.
  - d. Patients  $\geq 18$  years of age.
  - e. Patients with Eastern Cooperative Oncology Group (ECOG) performance status of 0 or 1.
  - f. Patients with measurable disease by CT or MRI per RECIST v.1.1 criteria.
  - g. Patients with Radiographic Tumor Assessment performed within 30 days of randomization.
  - h. Target lesions may be located in a previously irradiated field if there is documented (radiographic) disease progression at that site.
    - i) Target lesions may be located in a previously irradiated field if there is documented (radiographic) disease progression at that site.
  - i. Patients that have completed prior radiotherapy or radiosurgery at least 2 weeks prior to randomization.

- i) Patients with brain metastases are eligible if they are asymptomatic, are treated, or are neurologically stable for at least 2 weeks without the use of steroids or on stable or decreasing dose of  $\leq 10$  mg QD prednisone (or equivalent).
- j. Patients with baseline laboratory values obtained 21 days prior to randomization meeting the following criteria:
  - i) WBCs  $\geq 2000/\mu\text{L}$ .
  - ii) Neutrophils  $\geq 1500/\mu\text{L}$ .
  - iii) Platelets  $\geq 100 \times 10^3/\mu\text{L}$ .
  - iv) Hemoglobin  $\geq 9.0$  g/dL.

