### **7.5 Tumor Assessments**

- CT or MRI (if allergic to contrast media) scans will be performed every 8 weeks ( $\pm 7$  days) during the study treatment and during the first year from discontinuation of the study treatment, every 12 weeks ( $\pm 7$  days) during the second year, and every 16 weeks ( $\pm 7$  days) thereafter, to evaluate response to treatment by RECIST v.1.1.
- The same radiographic procedure (includes head and CAPs) to define measurable lesions must be used throughout the trial for each patient.
- Patients will continue the assigned trial treatments until tumor progression (by RECIST v.1.1 criteria) by CT or MRI (if allergic to contrast media), withdrawal from the trial, or intolerance of therapy not manageable with dose modifications outlined in the protocol/package insert and/or supportive care. Note: patients with suspected radiographic pseudoprogression, in the absence of clinical deterioration, should remain on trial treatments and be rescanned at 4 weeks or later. If progression is confirmed on follow-up scan, study treatments will be discontinued or patients on Arm 2 may be eligible for crossover. Refer to Section 7.6.
- Patients who discontinue trial treatments with response of CR, PR, or SD will undergo CT or MRI scan evaluations per protocol until time of PD, death, study completion, or initiation of subsequent anti-cancer therapy, whichever is first.
- Patients who demonstrate clinical progression before their scans are due will have an unscheduled scan conducted to document disease status by RECIST v.1.1.
- The first scheduled tumor response assessment will be performed at 8 weeks ( $\pm 7$  days), and responders (CR or PR per RECIST v1.1) will have a confirmatory scan at  $\geq 4$  weeks after response has been established using the same technique as baseline scans.
- All CT/MRI scans for all patients randomized on the trial will be collected prospectively and submitted to a central imaging vendor for archiving. These scans may be independently reviewed at a later time at the request of Lilly.

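### The PFS censoring note gives two conflicting tests for two missed scans, and its 119-day test can censor an event at randomization after a single missed scan

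*SAP*

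**What the plan says.** **SAP Table JZGD.6.1.** Rule 7 censors a progression or death that follows two or more consecutive missed post-baseline assessments. The censoring date is "Date of last adequate tumor assessment before missed assessment or date of randomization, whichever is later". When several rules apply, the earliest date decides both time and outcome.

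The Note defines the trigger twice. In words: "Two consecutive post-baseline tumor assessments refers to the next 2 protocol scheduled tumor assessments". In numbers: "Time is measured from the last adequate tumor assessment date", "the window allowed for each scan is 7 days", and a patient who goes beyond 2×7×8+7 = 119 days "is considered missing 2 consecutive assessments) in the first year".

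Two other rules in the table matter here. Rule 9 has the same situation text as Rule 7 but another censoring date: "Date of last adequate tumor assessment before the start of new anti-cancer therapy". Rule 1 censors at randomization when there is no baseline scan and, unlike Rule 2, does not require that the patient has not died.

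**Protocol.** Section 4.1 requires "Patients with Radiographic Tumor Assessment performed within 30 days of randomization", and Section 7.3 repeats the 30 days. Appendix D says 4 weeks before Day 1. The synopsis says 3 days, or 30 days for a standard-practice scan. Under Section 7.5 the first response scan is at Week 8, and scans are every 8 weeks (±7 "days) during the study treatment and during the first year from discontinuation of the study treatment". Section 10.2.2 counts a death without reported progression as an event on its date, and lets the SAP add censoring rules.

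**The concern.** The scan schedule runs forward from the start of the study, but the 119-day clock can start at a baseline scan taken weeks earlier. Those extra days use up the allowance, so the limit can expire while only one scheduled scan has been missed. An observed progression or death then becomes a patient with no follow-up time at all.

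Patients who miss a scan and then progress or die are unlikely to be missing at random. With about 25 per arm, each lost event shows in the Kaplan-Meier estimates, the 3-monthly rates and the restricted mean difference of SAP Section 6.5.3.1. None of the three PFS sensitivity analyses in SAP Section 6.5.5.1 lifts the rule. They deal with clinical progression, unconfirmed pseudoprogression and subsequent therapy.

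**Working it through.** Days are counted with randomization as day 0. If visits are instead counted from first dose, which may be up to 3 days later (synopsis), the gaps grow by up to 3 days.

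**The plan's figure.** 2 × 56 + 7 = 119 days, reproduced. It contains one 7-day window.

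**Scheduled windows.** Week 8 is days 49-63, Week 16 is days 105-119, and Week 24 is days 161-175.

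**Baseline is the only adequate scan.** With baseline b days before randomization, the limit falls on day 119 − b. The gap at a Week 16 scan on day s is s + b.

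| b | Limit falls on day | Gap at scan on day 105 / 112 / 119 | Over 119? |
|---|---|---|---|
| 0 | 119 | 105 / 112 / 119 | none |
| 3 | 116 | 108 / 115 / 122 | late scan only |
| 7 | 112 | 112 / 119 / 126 | late scan only |
| 8 | 111 | 113 / 120 / 127 | on-time and late |
| 15 | 104 | 120 / 127 / 134 | all |
| 28 | 91 | 133 / 140 / 147 | all |
| 30 | 89 | 135 / 142 / 149 | all |

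An on-time Week 16 scan is therefore caught when b ≥ 8, and any in-window scan when b ≥ 15. With b = 30, a death without a post-baseline scan is caught from day 90 (with b = 28, from day 92), although the Week 16 window opens only on day 105. Rule 7 then gives randomization as the censoring date, and the earliest-date rule lets it override the event.

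**Share caught among patients who missed only Week 8 and have the event at an in-window Week 16 scan.** The documents do not give the distribution of baseline dates. I assume it is uniform over 1 to B days before randomization, with the Week 16 scan uniform over its window:
- B = 3: 6 of 45 combinations, 13% (0% if the scan is exactly on time)
- B = 14: 50%
- B = 21: 67%
- B = 28: 75%
- B = 30: 77% (on-time scan: 23/30)

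**Number of patients.** Assume 5-10% of 25 per arm miss only Week 8, which is 1.25-2.5 patients, and that all of them have an event at Week 16.
- At 77%: 1.25 × 0.77 = 0.96 to 2.5 × 0.77 = 1.9 per arm
- At 50%: 0.6 to 1.25
- At 13%: 0.2 to 0.3
- If only half have an event at Week 16, the 77% figures fall to about 0.5-1
- The count scales with the miss rate: 20% would give 5 × 0.77 = 3.8

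**After a post-baseline scan.** Take a Week 8 scan on day 49, Week 16 missed, and progression at Week 24 on days 169-175. The gap is 120-126 days, over the limit with one miss. This needs an early and a late deviation that add to more than 7 days: 28 of 225 combinations (12%) if uniform, about 4% if deviations have an SD of 3 days (both assumed). Censoring here is at the last scan, not at randomization.

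**The opposite error.** After an extra scan on day 84 the limit is 84 + 119 = day 203, although the next two scheduled windows have closed by day 175.

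**The case against.** The strongest reply is that the verbal definition governs and 119 days is only an example. On the verbal test, a patient who missed Week 8 and was scanned at Week 16 has not missed two assessments and stays an event. This stands in part: the defect is a conflict between two tests, not a single settled rule. But the sentence that starts the clock at the last adequate scan is a rule of its own and makes no exception for baseline. Rule 7's fallback to randomization has effect only if that scan can precede randomization. The 119 days is also the only number a programmer is given.

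It is also fair that PFS is secondary, that all analyses are descriptive, that the primary ORR is untouched, and that the protocol allows added censoring rules. Rule 1 should almost never apply, since eligibility requires a baseline scan and no waivers are granted (Protocol Sections 4.0 and 4.1).

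A reader might infer more than the documents support:
- **That PFS is biased upward throughout.** Censoring a day-112 event at randomization takes the patient out of the risk set, so the curve is lower before day 112 and higher after it. The protocol background cites nivolumab median PFS of 2.3 and 3.5 months (about 70 and 107 days at 30.4375 days per month). If the arms behave similarly, a median before day 112 would stay the same or fall.
- **That the earliest deaths are lost.** Even with baseline on day −30, nothing up to day 89 is removed by this route.
- **That duration of response is censored at randomization.** Responders have a post-baseline scan by definition, so only the early-then-late case can reach them.
- **That a particular wrong limit applies after year one.** The Note ties its figure to the first year, while 8-weekly scans last for all of treatment and a year beyond. No document states another limit, so this is a gap in the Note.

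**Conclusion.** The Note contains two tests that give different answers, and the numeric one is wrong for a patient who missed only Week 8 after a baseline scan taken well before randomization. The conditions are specific: no post-baseline scan before the event, and a gap beyond 119 days. For an on-time Week 16 progression that means baseline at least 8 days before randomization.

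The size is probably no more than about 1-2 patients per arm. This rests on an assumed 5-10% miss rate, on uniform baseline dates over the full 30 days, and on every such patient having an event at Week 16. If most baseline scans fall within 3 days of randomization, it is near zero. To say that events are often censored at randomization would go beyond the documents, which give neither the miss rate nor the baseline timing. The early-then-late case is rarer and milder.

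The point deserves correction because a stated rule gives a wrong result in a small trial, no planned sensitivity analysis would show it, and the repair is simple.

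**What to change.** Revise the Note and two rules of SAP Table JZGD.6.1:
1. Start the clock at the later of randomization and the last adequate scan. With no post-baseline scan the 119-day limit then falls on day 119, the close of the Week 16 window, and no in-window Week 16 scan exceeds it.
2. Define two missed assessments directly: the next two scheduled scan windows have both passed without an adequate scan. This replaces the day count. A flat 126 days (2 × 56 + 14) would cure the early-then-late case, but would move the limit after a day-84 scan from day 203 to day 210.
3. Use the interval in force under Protocol Section 7.5: 8-weekly for all time on treatment and the first year off treatment, then 12-weekly, then 16-weekly.
4. Add to Rule 1 the condition in Rule 2 that the patient has not died.
5. Delete Rule 9 or reconcile it with Rules 7 and 8. Its censoring date is undefined if no new therapy was started, and rewording it to cover events after new therapy would duplicate Rule 8.

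The cost is SAP wording and a small change to the derivation program. No patient procedure changes. Any PFS output already produced would need to be rerun.
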